6.1. Reporting Guidelines

We will follow the Consolidated Standards of Reporting Trials (CONSORT) 2010 statement: updated guidelines for reporting cluster randomised trials (<http://www.consort-statement.org/>).

6.2. Participant Disposition and Flow Chart

A flow chart will be drawn up showing the number of participants screened, enrolled, and followed-up in each study arm, and the number contributing to the ITT and PP analyses.

The number screened and not enrolled and the reasons for non-enrolment will be reported, as well as the number and reasons of participants who were lost to follow up, or who were withdrawn from study for safety reason, or who crossed-over between study arms, or because of other reasons, et al.

A list of major protocol deviations will be presented after being unblind.

6.3. Data Summaries

Continuous variables will be summarized according to number of subjects with non-missing data (n), mean, standard deviation (SD), median, minimum, and maximum. The confidence intervals will be reported on summaries of continuous effectiveness variables.

Categorical variables will be summarized according to the absolute frequency and percentage of subjects (%) in each category level. The denominator for the percentages is the number of subjects in the treatment arm with data available, unless noted otherwise.

6.4. Graphical Displays

Mean values for some continuous outcomes by treatment and visit will be plotted.

6.5. Multiplicity

Multiplicity adjustment will not apply to the primary and secondary outcome analyses.

6.6. Missing Data

Missing baseline covariates will be imputed using simple imputation methods in the covariate adjusted analysis based on the covariate distributions, should the missing values for a particular covariate be less than 5%. For a continuous variable, missing values will be imputed from random values from a normal distribution with mean and SD calculated from the available sample. For a categorical variable, missing values will be imputed from random values from a uniform distribution with probabilities P_1, P_2, \dots , and P_k from the sample. Seed for the imputation will be set as 128.

If the missing values for a covariate are $\geq 5\%$ then they will be imputed using Markov chain Monte Carlo (MCMC) methods using SAS PROC MI.

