5.1.2. Sensitivity analyses of the primary outcome

- **PP analysis of the primary outcome**

The same analysis of the primary outcome will be performed in the PP population using a GEE model (described in 5.1.1).

- **Covariate adjusted analysis of the primary outcome**

A GEE model used for the analysis of the primary outcome in Section 5.1.1 will also be used for covariate adjusted analysis using inverse probability of treatment weighting (IPTW) approach. The covariates will include age (continuous variable), ethnic (binary variable), body mass index (continuous variable), adverse pregnant history (binary variable), parity (continuous variable), exposure to smoking (mother or father's smoking status, binary variable), total cholesterol (continuous variable), and RBC folate level (continuous variable) at baseline to estimate adjusted risk ratio and 95% CI. Covariate adjusted analysis will be performed on both ITT and PP populations.

We will first calculate a propensity score with treatment as the dependent variable (1 for the experimental group and 0 for the reference group), and all covariates listed above as independent variables through a logistic regression model with a random effect for the center, and then perform an IPTW analysis (weighted GEE model). The adjusted risk ratio between the two groups and its two-sided 95%CI will be estimated.

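### Section 6.6 fills covariates with under 5% missing by one unconditional random draw, which adds seed noise and weakens the adjusted sensitivity analysis slightly; one multiple imputation for all covariates would do better at little cost

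*SAP*

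**What the plan says.** SAP section 6.6 sets two rules for missing baseline covariates and limits both to the covariate-adjusted analysis.

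- **Below 5%.** The simple rule applies "should the missing values for a particular covariate be less than 5" per cent. On continuous covariates the text reads "missing values will be imputed from random values from a normal distribution with mean and SD calculated from the available sample". Categorical covariates have their own sentence, which begins "For a categorical variable, missing values will be imputed from random values from a uniform distribution with probabilities" and means the observed proportions. A single seed is fixed in advance: "Seed for the imputation will be set as 128". No repeated draws and no added variance are mentioned.
- **At 5% or more.** The values are "imputed using Markov chain Monte Carlo (MCMC) methods using SAS PROC MI". The text makes no distinction by variable type. It gives no number of imputations, no list of variables for the imputation model and no combining rule.

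The analysis served is in SAP section 5.1.2: the GEE of the primary outcome "will also be used for covariate adjusted analysis using inverse probability of treatment weighting (IPTW) approach". It has eight covariates. Three are binary (ethnicity, adverse pregnancy history, smoking exposure). Five are treated as continuous (age, body mass index, parity, total cholesterol, RBC folate); parity is so labelled in "adverse pregnant history (binary variable), parity (continuous variable"). Section 5.1.1 bases the main conclusion on a GEE with treatment as the only predictor.

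**The concern.** The adjusted analysis is there to show whether baseline imbalance between the arms, with only 22 clusters, could explain the primary result. A draw from the marginal distribution carries no information about the woman it is assigned to. Weighting on it leaves her true covariate value unbalanced and adds noise to the propensity model. Because only one draw is made, the analysis treats the filled value as observed.

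The limit does not cap the total. Each covariate can pass it alone while many women carry at least one random value.

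The rule from 5% upwards has a different weakness. The MCMC method of PROC MI uses a multivariate-normal model. That is a property of the software method; the SAP does not say it. Applied to binary covariates, it returns values that are neither 0 nor 1.

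**Working it through.** The SAP gives no figure for this point, so there is none to reproduce. It states no missing rates, covariate distributions or size of imbalance; those used below are assumptions.

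**1. Women with at least one random value.** With eight covariates, each missing in a share q independently, the share is 1 − (1 − q)^8.
- q = 1%: 8%
- q = 3%: 22%
- q = 4.9%: 33%
- q = 5%: 1 − 0.95^8 = 34%

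**2. Adjustment kept, by algebra.** Take standardised covariates with equal arm differences d and pairwise correlation r, missing completely at random. Z is the filled covariate. Under either fill the arm difference in Z is (1 − q)d. The part of the true imbalance removed is that difference times the slope of the true covariates on the filled ones.
- Random draw, r = 0: Z has variance 1 and covariance (1 − q) with the true value, so the slope is 1 − q. Kept: (1 − q)² = 0.951² = 0.904.
- Mean fill, r = 0: variance and covariance are both 1 − q, so the slope is 1. Kept: 1 − q = 0.951.
- Random draw, r = 0.2: (1 − q)²(1 + 7r)/(1 + 7r(1 − q)²) = 0.9044 × 2.4/(1 + 1.4 × 0.9044) = 0.958.
- Mean fill, r = 0.2: (1 − q)(1 + 7r)/(1 + 7r(1 − q)) = 0.951 × 2.4/(1 + 1.4 × 0.951) = 0.979.

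Simulations of the weighted estimate agree: about 90% against 95% with independent covariates, and 96 to 97% against 98 to 99% at correlation 0.2. Mean fill loses about half as much as the random draw, but it does lose some.

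**3. Effect on the risk ratio (RR).** Simulated trials had 22 clusters of 111, eight covariates of the SAP's types, a true RR of 0.5 and 4.9% missing in every covariate. The propensity model was a plain logistic one, without the SAP's random centre effect.
- Imbalance 0.3 SD: unadjusted 0.6093, full data 0.5128, SAP draw 0.5192. Share of adjustment lost: ln(0.5192/0.5128)/ln(0.6093/0.5128) = 0.0124/0.1724 = 7%. The RR moves by about 1%.
- Imbalance 0.5 SD, with stronger covariate effects: unadjusted 0.8195, full data 0.4969, SAP draw 0.5168. Lost: 0.0393/0.5003 = 8%. The RR moves by about 4%.
- Only one covariate missing: about 2.5% of the adjustment is lost.
- Multiple imputation conditional on the other covariates, arm and outcome, in the 0.3 SD case: 0.513, the full-data value.

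**4. Seed noise.** The SD of log RR over 100 seeds was 0.0035 (one covariate, 3% missing) to 0.011 (all eight, 4.9% missing). The sampling SD was about 0.20, so the largest seed variance is (0.011/0.20)² = 0.3% of the sampling variance.

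**5. Normal model for binary covariates.** About 35% of imputed binary values fell outside 0 to 1. The log RR differed from full data by 0.001 (SE 0.002) at 4.9% missing and 0.001 (SE 0.003) at 10%.

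**The case against.** The strongest defence is that nothing of consequence changes. The main conclusion comes from the unadjusted GEE, and the imputation serves one sensitivity analysis. The shift in RR is about 1% at 0.3 SD imbalance even with all eight covariates at the limit. All of this stands.

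Four stronger readings are tempting, and the documents do not support them.

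- *The result could be chosen through the seed.* It could not. The seed is fixed in advance, so the result is reproducible. What remains is that one draw carries no imputation uncertainty.
- *Impossible values distort the RR.* Fractional parity and out-of-range binary values enter only as regressors in the propensity model, and no bias appeared in simulation.
- *A fifth to a third of filled parity values would be negative.* That needs a mean parity of 0.2 to 0.5 with SD 0.42 to 0.6. Table 1 in SAP section 7 lists parity as 1 or at least 2, with no zero class. Moving those means up by one, to 1.2 to 1.5, leaves about 0.2 to 0.6% negative. Fractional values and values below 1 would remain.
- *Mean fill would restore the full adjustment.* It would not. A woman given the overall mean also has her true value ignored.

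It may also be said that the choice of imputation method is a matter of taste. That carries some weight at this size of effect. But the random draw is worse than mean fill both on noise and on adjustment kept, and it offers nothing in return.

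**Conclusion.** The point holds as a minor one. Below 5% missing, the prescribed draw adds avoidable noise, carries no imputation uncertainty and gives up some of the adjustment. The loss is about 10% in the worst case (eight independent covariates, each 4.9% missing completely at random), 3 to 4% at correlation 0.2, and about 2.5% when only one covariate is affected. Mean fill loses about half as much, and conditional multiple imputation recovered the full-data RR. The 34% of women is an upper figure that needs all eight covariates at the limit with independent missingness.

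The lost adjustment was shown only for the rule below 5%. The rule from 5% upwards fits three covariates poorly and leaves its execution open, but no bias in the RR was found. The primary analysis is unaffected.

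**What to change.** Replace both rules in section 6.6 with one multiple imputation, used at any missing share. Use fully conditional specification in PROC MI: logistic models for ethnicity, adverse pregnancy history and smoking exposure, and predictive mean matching for parity and the skewed continuous covariates. Put arm, centre and primary outcome in the imputation model. Because arm is fixed within centre, centre indicators already contain it, so the SAP should state how both are entered. Fit the propensity model and the weighted GEE in each imputed set, pool by Rubin's rules, and state the number of imputations and the seed.

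If a simple rule is kept below 5%, use the overall mean for a continuous covariate with a missing indicator, and a missing category for a categorical one. This is acceptable because the covariates precede the intervention. It needs no seed and loses about half as much adjustment or less, but it does not restore it fully. If the categorical draw is kept, drop the word "uniform", since a uniform distribution has equal probabilities.

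The cost is a change of SAP wording and a few lines of code, with slightly more computation and no new data.

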7. TABLE CONTENTS

Table 1: Summary statistics of baseline information.

Variable	Statistics	Treatment A (N=)	Treatment B (N=)	All (N=)
Age (year)	n			
	Mean			
	SD			
	<35			
	≥35			
Ethnicity	n			
	Han			
	Other			
Preconception Body Mass Index, kg/m ²	n			
	Mean			
	SD			
	<24 kg/m ²			
	≥24 kg/m ²			
Parity, time	n			
	1			
	≥2			
Presence of adverse pregnant history	n			
	Yes			
	No			
Exposure to smoking	n			
	Yes			
	No			

Table 2: Summary statistics of compliance of participants.

Variable	Statistics	Treatment A (N=)	Treatment B (N=)	All (N=)
RBC folate concentration before pregnancy	n			
	Mean			
	SD			
	Median			
	IOR			
<400 ng/ml	n(%)			
≥400 ng/ml	n(%)			
RBC folate concentration at the first antenatal visit	n			
	Mean			
	SD			
	Median			
	IQR			
<400 ng/ml	n(%)			
≥400 ng/ml	n(%)			

Table 3: Summary statistics of primary and secondary outcomes estimated by GEE model.

Primary and secondary binary outcomes	N(%)		GEE model analysis	
	Treatment A (N=)	Treatment B (N=)	Risk Ratio (95%CI)	p-value
Occurrence of fetus defects, still birth, and birth defects				
Occurrence of fetal defects				
Occurrence of birth defects				
Occurrence of abortion that related with congenital defects				
Occurrence of gestational hypertension				
Occurrence of maternal gestational diabetes				

Table 4: Summary statistics of secondary repeated measured outcomes estimated by linear mixed model.

Secondary repeated measured outcomes	Visit	n, mean (SD)		Mixed model analysis		
		Treatment A (N=)	Treatment B (N=)	A vs. B Mean difference (95%CI)	p-value	P-value from Treatment*time interaction test
Baby body weight	Birth					
	42 days					
	3 months					
	6 months					
Maternal body weight during gestation	Periconception					
	Gestational week 20					
	At delivery					

9. APPENDIXES

9.1. Appendix 1. Types of fetus defects and birth defects

1. Anencephalus
2. Spina bifida
3. Encephalocele
4. Congenital Hydrocephalus
5. Cleft Palate
6. Cleft Lip
7. Cleft Lip with Cleft Palate
8. Microtia (including Anotia)
9. Deformity of external ear(s) (except Microtia and Anotia)
10. Esophageal atresia or stenosis
11. Anorectal atresia (including Congenital Anorectal Malformations)
12. Hypospadias
13. Ectopocystis
14. Pes Equinovarus
15. Polydactylism
16. Syndactylia
17. Limb shortening
18. Congenital Diaphragmatic Hernia
19. Peromphalus
20. Celoschisis
21. Conjoined Twins
22. Trisomy 21 syndrome
23. Congenital heart disease
24. Others.

9.2. Appendix 2. FOID Study variable list

Appendix 2.1 Intervention trial variable list

NO	variable	
Pre-pregnancy		
1	hospital card number	T
2	Recruited number	T
3	Recruited date	D
4	Female name	T
5	Female height	N
6	Female weight	N
7	Female age	N
8	Male name	T
9	Male height	N
10	Male weight	N
11	Male age	N
12	Tel No	T
13	Community (basis for grouping)	N
14	Nutrient Interventions	B (1=intervention 0=control)
Nutrient first test		
15	Nutrient first test date	D
16	Serum folate	N
17	Red blood cell folate	N
18	Serum ferritin	N
19	VD(Vitamin D)	N
20	HCY(homocysteine)	N
21	Vitamin B12	N
22	LDL low density lipoprotein cholesterol	N
23	HDL high density lipoprotein cholesterol	N
24	TG total cholesterol	N
25	TC triglyceride	N
26	FBG(fasting blood-glucose)	N
27	Genotyping (BHMT (rs3733890), CBS (rs2850144, rs2851391), FIGN (rs2119289), MTHFD1 (rs2236225), MTHFR (rs1801131, rs1801133, rs3737965), MRT (rs1805087, rs28372871, rs1131450), MTRR (rs1801394, rs326119), RFC1 (rs1051266), and SHMT (rs1979277))	B
28	Clinical information (see Table 3)	-
29	Insufficient serum folate	B
30	Insufficient RBC folate	B

	Nutrient repetition measurement	
29	Nutrient repetition measurement date	D
30	Serum folate	N
31	Red blood cell folate	N
32	HCY (Homocysteine)	N
	Pregnancy	
33	Ultrasound image screen in mid-gestation	T
34	Report detail (positive)	B
35	Confirm image diagnosis	T
36	Therapeutic plan	T
37	birth defect diagnosis	T
38	Clinical information (see Table 2)	-

Note: T, text variable; D, The date type; N, Continuous variable; B, binary variable.

Appendix 2.2 Pregnant variable list in routine system

NO	variable	
	Basic information	
1	hospital card number	T
2	inpatient number	T
3	name	T
4	age	N
5	Pregnant times	N
6	Delivery times	N
7	last menstrual period	D
8	Gestational week at the first visit	N
9	The first visit date	D
10	Height	N
11	Weight	N
12	Systolic blood pressure at the first visit	N
13	Diastolic blood pressure at the first visit	N
14	Occupation	T
15	Education	T
	Antenatal care record	
16	Weight at each antenatal care	N
17	Systolic blood pressure at each antenatal care	N
18	Diastolic blood pressure at each antenatal care	N
19	Gestational week at each antenatal care	N
20	Antenatal care date	D
	Lab data	
21	Cytomegalovirus	N
22	Cytomegalovirus date	D
23	Rubella virus	N
24	Rubella virus date	D
25	Toxoplasmosis	N
26	Toxoplasmosis date	D
27	Syphilis screening	N
28	Syphilis screening date	D
29	Fasting blood-glucose	N
30	Fasting blood-glucose date	D
31	HCT(hematokrit)	N
32	HCT(hematokrit) date	D
33	Serum folate	N
34	Serum folate date	D
35	HCY(homocysteine)	N
36	HCY(homocysteine) date	D

37	OGTT 0 hours	N
38	OGTT 1 hours	N
39	OGTT 2 hours	N
40	OGTT date	D
41	Triglyceride	N
42	Triglyceride date	D
43	Total cholesterol	N
44	Total cholesterol date	D
45	Hemoglobin date	N
46	Hemoglobin date	D
	Delivery date	
47	Gestational week at delivery	N
48	Delivery mode	T
49	Birth weight	N
50	Birth weight(second baby)	N
51	Systolic blood pressure at delivery	N
52	Diastolic blood pressure at delivery	N
53	Apgar scoring	N
54	Delivery date	D
55	Birth defect records	T
56	Weight blood pressure at delivery	N

Note: The data will be extracted from maternal clinic antenatal medical record system.

T, text variable; D, The date type; N, Continuous variable; B, binary variable.

Appendix 2.3 Pre-pregnant variable list in routine system

	variable	
	Basic information	
1	Wife id	T
2	Husband nation	T
3	Husband age	N
4	Husband education	T
5	Husband id	T
6	Husband occupation	T
7	Wife nation	T
8	Wife age	N
9	Wife education	T
10	Wife occupation	T
11	Tel no	T
12	Mobile phone No	T
	Medical history	
13	Female anemia	B
14	Female EH	B
15	Female heart disease	B
16	Female DM	B
17	Female epilepsy	B
18	Female thyroid disease	B
19	Female CGN	B
20	Female mental disease	B
21	Female tumour	B
22	Female TB	B
23	Female HBV	B
24	Female VD	B
25	Male anemia	B
26	Male EH	B
27	Male heart disease	B
28	Male DM	B
29	Male epilepsy	B
30	Male thyroid disease	B
31	Male CGN	B
32	Male mental disease	B
33	Male tumour	B
34	Male TB	B
35	Male HBV	B
36	Male VD	B
	Vaccine	
37	Female rubella vaccine	B
38	Female hepB vaccine	B

39	Male hepB vaccine	B
	Durg	
40	Female current medicine	B
41	Female medicine name	B
42	Male current medicine	B
43	Male medicine name	B
	Childbearing history	
44	Birth history	B
45	Pregnancy times	B
46	Live birth	B
47	Dead fetus	B
48	Dead birth	B
49	Term delivery	B
50	Premature delivery	B
51	Natural abortion	B
52	Abactio	B
53	Children number	B
54	Birth defect	B
55	Defect type	B
56	Menarche age	B
57	Period menstruation	B
58	Menstrual cycle	B
59	Menstrual quantity	B
60	LMP	D
	Family history of disease	
61	Female family history thalassemia	B
62	Female family history albinism	B
63	Female family history favism	B
64	Female family history hemophilia	B
65	Female family history CHD	B
66	Female family history DS	B
67	Female family history openNTDs	B
68	Female family history DM	B
69	Female family history dysnoesia	B
70	Female family history daysaudia	B
71	Female family history viaual disorder	B
72	Female family history neuropsychiatric	B
73	Female family history other birthdefects	B
74	Female family history fetal death	B
75	Female family history intermarry	B
76	Female family history relations	B
77	Male family history thalassemia	B
78	Male family history albinism	B

79	Male family history favism	B
80	Male family history hemophilia	B
81	Male family history CHD	B
82	Male family history DS	B
83	Male family history openNTDs	B
84	Male family history DM	B
85	Male family history dysnoesia	B
86	Male family history dysaudia	B
87	Male family history viaual disorder	B
88	Male family history neuropsychiatric	B
89	Male family history other birth defects	B
90	Male family history fetal death	B
91	Male family history intermarry	B
92	Male family history relations	B
Anthroposomatology		
93	Female height	N
94	Female weight	N
95	Female BMI	N
96	Female heart rate	N
97	Female SBP	N
98	Female SDP	N
99	Male height	N
100	Male weight	N
101	Male BMI	N
102	Male heart rate	N
103	Male SBP	N
104	Male SDP	N
Lab data		
105	Leucorrhea check	N
106	Clue cell	N
107	Monilia infection	N
108	Trichomomas	N
109	Cleanness	N
110	Whiff test	N
111	PH	N
112	Wom blood analysis	N
113	Female hb	N
114	Female wbc	N
115	Female rbc	N
116	Wom urine test	N
117	Female ABO	N
118	Female Rh	N
119	Female GLU	N

120	Female GLU levels	N
121	Female NG	N
122	Female chlamydia	N
123	Female syphilis	N
124	Female HIV	N
125	Female ALT	N
126	Female ALT levels	N
127	Female HBs-Ag	N
128	Female HBs-Ab	N
129	Female HBe-Ag	N
130	Female HBe-Ab	N
131	Female HBc-Ab	N
132	Female HCV-Ab	N
133	Female CMV IgM	N
134	Female CMV IgG	N
135	Female RV IgM	N
136	Female RV IgG	N
137	Female TOX IgM	N
138	Female TOX IgG	N
139	Male blood analysis	N
140	Male hb	N
141	Male wbc	N
142	Male rbc	N

Note: The data will be extracted the preconception care electronic data system T, text variable; D, The date type; N, Continuous variable; B, binary variable.
